Appendix 3: Laboratory Results Form _Visit N°: ____ (Attach results to the form)

Patient's initials: _____ Pt file N° _____	Data clerk Initials: _____
Visit N°: _____	Date data entry: ____ - ____ - ____ (dd-mm-yyyy)
Name of interviewer: _____	

Hepatitis C Test	
420_ HCV Viral Load ____ . ____ . ____ IU/ mL	421_ DATE ____ - ____ - ____ (dd-mm-yyyy)
	421_  If HCV VL undetectable
422_ Genotype _____ Sub-type _____	423_ DATE ____ - ____ - ____ (dd-mm-yyyy)
424_ Fibroscan kPA . ____ . ____	425_ DATE ____ - ____ - ____ (dd-mm-yyyy)
426_ Validity % ____	427_ Staging Category F _____
428_ Liver Biopsy Metafavar score _____	429_ DATE ____ - ____ - ____ (dd-mm-yyyy)

430_ APRI score: _____ calculated by clinician (calculated also in the database)
431_ Child Pugh score: _____ calculated by clinician (calculated also in the database)

HIV associated tests	
432_ CD4 count ____ cells/μL	433_ DATE ____ - ____ - ____ (dd-mm-yyyy)
434_ Viral Load ____ . ____ . ____ copies/mL	435_ DATE ____ - ____ - ____ (dd-mm-yyyy)
 If HIV VL undetectable	
436_ HIV diagnosis tests (According to national guidelines)	437_ DATE ____ - ____ - ____ (dd-mm-yyyy)
 Positive	 Negative
 Indeterminate	

Miscellaneous Tests	
438_ Pregnancy Test	439_ DATE ____ - ____ - ____ (dd-mm-yyyy)
 Positive	 Negative
440_ Proteinurie	441_ DATE ____ - ____ - ____ (dd-mm-yyyy)
Results :  +  ++  +++  ++++	
442_ HBV test Ag HbS	443_ DATE ____ - ____ - ____ (dd-mm-yyyy)
 Positive	 Negative

1_Surname: _____	2_Forename: _____ (not to enter in the database)
Patient's file N° _____	
3_ Identification cohort Number: _____	4_ID Key _____

5_Date of consultation: ____ - ____ - ____ (dd-mm-yyyy)	7_Name of interviewer: _____	9_Data clerk initials: _____
6_Site of consultation: _____		10_Date of data entry: ____ - ____ - ____ (dd-mm-yyyy)

Instructions: *Complete only for the received results. Circle the correct Unit.*
If the answer is unknown, tick the box DK (don't know)
*The requested date is the **date of the blood taken**.*
*Please refer carefully to the laboratory results and **mark the laboratory results form with the Visit N°***

Hematology	401_DATE	____ - ____ - ____ (dd-mm-yyyy)
402_Erythrocytes (RBC) __, __	10 ⁶ / μL	
403_Leukocytes (WBC) ____, __	10 ³ / μL	
404_Neutrophils _____	10 ³ / μL	or Neutrophils _____ %
405_Platelets _____	10 ³ / μL	
406_Haemoglobin ____, __	g/dL	

Coagulation tests	407_DATE	____ - ____ - ____ (dd-mm-yyyy)
408_Quick Test _____ %	409_INR	____. ____ (no unit)

Biochemistry	410_DATE	____ - ____ - ____ (dd-mm-yyyy)
411_ALT _____ IU/L		Circle the correct Unit.
412_AST _____ IU/L	417_Glucose	_____ mg/dL
(413_AST upper limit reference _____ IU/L)	418_Creatinine (serum)	_____ mg/dl
414_Albumin _____ g/dl	419_TSH	_____ μU/ml
415_Total Bilirubin _____ mg/dL		
416_Direct Bilirubin (conjugated) _____ mg/dL		

Minimum laboratory follow-up schedule

Table 3.0 Schedule of consultation and of laboratory follow-up

Examination	Baseline	Pre-treatment ³	Ongoing Monitoring (weeks of Treatment)									12 wks after Rx	
			1	2	3	4	8	12	16	20	24		
Clinical Evaluation	X	X	X ⁵	X	X ⁵	X	X	X	X	X ^{6,7}	X ^{6,7}	X ⁷	X
HBsAg	X												
Complete blood count	X	X		X ⁸		X ⁸	X ⁸	X ⁸					
Haemoglobin				X		X	X	X	X ⁷	X ⁷		X ⁷	
CD4 count	X							X ⁹				X ⁹	
INR ¹	X												
ALT	X	X		X		X		X				X ⁷	X
AST ¹	X	X											
Creatinine, Creatinine clearance		X		X		X		X				X ⁷	
Bilirubin total ¹	X	X						X				X ⁷	
Albumin ¹	X	X				X		X					
Glucose	X					X							
TSH ²	X							X ²					
HCV Viral Load	X	X ⁴				X ⁶		X ⁹				X ⁹	X
HCV Genotype	X												
HIV Viral Load	X							X ⁹				X ⁹	
Pregnancy Test		X				X	X	X	X ¹⁰	X ¹⁰		X ¹⁰	
FibroScan	X												

¹ required if METAVIR F4, APRI cut-off for cirrhosis;

² applies to PEG-INF containing therapy only;

³ all biochemical tests should be repeated if longer than three months from baseline examinations;

⁴ ONLY if longer than six months from baseline examination;

⁵ clinical evaluation during first month of treatment- additionally after 1st and 2nd week of treatment;

⁶ optional;

⁷ if treatment duration more than 12 weeks;

⁸ if PEG-INF containing regimen or decompensated cirrhosis (Child Pugh B-C) otherwise Hb alone is sufficient;

⁹ if end of treatment;

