4. OBJECTIVES

Primary objective

The primary objective of this study is to assess the effectiveness of HCV curative treatments in patients with chronic hepatitis C (CHC), co-infected with HIV in Manipur, India.

Secondary objectives

- a. To describe the demographic, clinical and biological characteristics of patients with chronic hepatitis C and HIV co-infection
- b. To assess the effectiveness of HCV curative strategies in patients with chronic HCV, co-infected with HIV stratified by regimen and by site
- c. To identify risk factors associated with differing virological responses
- d. To assess the safety of HCV treatment
- e. To monitor the safety of HCV treatment in HIV co-infected patients
- f. To document the clinical and biological tolerance of the HCV treatment
- g. To assess the feasibility of HCV treatment
- h. To assess comparative performance of elastography (Fibroscan®) and APRI (AST to Platelet Ration Index), to evaluate liver fibrosis among HIV/HCV co-infected individuals
- i. To describe causes of non-eligibility for treatment
- j. To describe the clinical and biological evolution of co-infected patients, not eligible for HCV treatment
- k. To assess treatment adherence

5. PRESENT KNOWLEDGE AND RELEVANT BIBLIOGRAPHY INCLUDING FULL TITLES OF ARTICLES RELATING TO THE PROJECT

The burden of hepatitis C worldwide is now being recognized as a major public health problem. An estimated 180 million people (~3% of the world's population) are chronically infected with the hepatitis C virus (HCV), responsible for 500,000 deaths each year (1, 2). Two thirds of those infected by Hepatitis C live in Africa or in Asia.

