Demographic and baseline characteristics of the patients will be described using summary statistics (mean with their 95% CI or median with inter-quantile intervals for continuous data; frequency and proportion for categorical data). It will include (but not be restricted to): - age - sex – treatment received - clinical signs at inclusion, haemoglobin and other biological measures at inclusion.

Depending of the distribution of the data, different tests and reports of results will be provided. Distributions of categorical variables between two groups will be compared with the Fisher's exact test or chi-squared. Comparisons of continuous variables will be performed with a 2-sample t-test when the variable shows a normal distribution; otherwise, a Wilcoxon rank sum test will be performed.

Risk factors associated with the different outcomes will be assessed using univariate and multivariate models. Epidemiological and clinical relevant variables will be included in the multivariate model to obtain an adjusted measure of association.

To assess the APRI performance, compared to Fibroscan®, for assessment of liver fibrosis among HIV/HCV coinfecting individuals, sensitivity, specificity, negative predictive value, positive predictive value will be computed, across liver fibrosis scores.

We will use an alpha level of 5% for all statistical tests. All statistical tests will be two-sided. All efficacy endpoints will be analyzed on the intent-to-treat (ITT) population during the cohort study (every year). The ITT population will include all subjects who were initiated under treatment (at least one prescription of HCV treatment).

Analyses will be performed using STATA, version 13 (StataCorp, College Station, Texas).

VI. Tools

Demographic and clinical data is currently collected via case reporting forms (CRFs) and laboratory forms. Data is collected on: individual baseline information, clinical evaluation information, laboratory results and treatment information. The CRFs are presented in Appendix 1-4. (All forms are currently being used for recording clinical management of new HCV patients entering treatment). De-identified data is entered in to an electronic database and used for reporting and monitoring and evaluation of HCV treatment activities.

Study participants will be linked through unique study numbers assigned to study participants. Personal identifier information will be recorded only on CRFs, and will be kept separately to maintain confidentiality.

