A HCV Genotype determination is performed to help determine the appropriate length and type of treatment in accordance with the most current WHO, Indian or other International guidelines. Genotyping has been performed by RT-PCR and sequencing with specimens sent to Babina laboratory in Imphal, Manipur. Due to concerns regarding the ability for this laboratory to differentiate between Genotype 1 and Genotype 6 with the given genotyping platform being used, further DBS samples will be sent to a Reference laboratory for quality control of genotype determination.

c). Other laboratory tests

The pre-treatment assessment and the follow-up of patients during treatment will require other laboratory tests at different time points, according also to the treatment regimen. The minimum schedule is presented in Table 3.0 of Appendix 3.

Laboratory tests are performed on site in Churachandpur with specimens sent to a reference laboratory in Babina for genotyping and viral load determination. Results of the different tests are collected on a specific CRF (CRF Lab results Form Appendix 3).

Elastography

Staging of the liver fibrosis and the calculation of the Metavir score will be determined by the elastography, using Fibroscan® 402 (Echosens, Paris) Training of field doctors in the use of this machine was conducted by trainers from Echosens during December of 2015.

The results will be interpreted according to the manufacturer recommendations. Results, including the validity score of the procedures which will be registered on the CRF Bio.

Plasma storage

Manipur will store plasma from consenting patients. Plasma is required in order to differentiate resistance profiles of the new DAA regimes, of which little is known. Additional tests on the plasma may be conducted in the case of failure of treatment, comparing viral profile before treatment to latter ones. In addition, as the transmission pathways are unclear, tests may be needed to differentiate relapse from re-infection during or after treatment. Therefore, the storage of samples will give the possibility to adapt medical care to the patients and adapt further the treatment regimen if indicated. Plasma will be stored for a period of five years.

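### Table 3.0 does not guarantee baseline AST below F4, so the APRI–FibroScan comparison in objective h may lack the patients it needs

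*Protocol*

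**What the plan says.** Section 4, objective h, reads "To assess comparative performance of elastography (Fibroscan®) and APRI (AST to Platelet Ration Index), to evaluate liver fibrosis among HIV/HCV co-infected individuals". The target population is the co-infected cohort and is not limited to patients with cirrhosis. Section 6.V adds that "sensitivity, specificity, negative predictive value, positive predictive value will be computed, across liver fibrosis scores", with FibroScan as the comparator.

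On how the two tests are obtained:

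- Section 6.VII, Elastography: "Staging of the liver fibrosis and the calculation of the Metavir score will be determined by the elastography".
- Appendix 3, Table 3.0: FibroScan, complete blood count (hence platelets) and ALT are marked at Baseline without condition. AST is marked at Baseline and Pre-treatment, but its row carries footnote 1, "required if METAVIR F4, APRI cut-off for cirrhosis". INR, total bilirubin and albumin carry the same footnote.
- The table is headed "Minimum laboratory follow-up schedule", and section 6.VII says "The minimum schedule is presented in Table 3.0 of Appendix 3".
- The laboratory form has fields for AST, for its upper limit ("413_AST upper limit reference") and for APRI, with no restriction by fibrosis stage. Its instruction is to fill in only results that have been received.

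**The concern.** An accuracy study needs the index test (APRI) in patients with and without the condition as defined by the comparator (FibroScan). Footnote 1 has two triggers for AST, and neither provides this. The first is F4, which is a positive result on the comparator. The second is an APRI value at the cirrhosis cut-off, which is circular because APRI cannot be calculated until AST has been measured.

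No other part of the protocol orders AST in patients below F4. If sites do what is required and no more, the patients needed for specificity and NPV have no APRI. If sites add AST at their discretion, who gets tested becomes part of the result. An analysis plan cannot repair this afterwards. For a treated patient, a pre-treatment AST that was never measured is lost.

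**Working it through.** **Inputs from the protocol.** Section 6.III gives about 1600 patients in care, 27% co-infection and 80% of seropositives chronic. 1600 × 0.27 × 0.80 = 345.6, which reproduces the stated minimum of 345. The protocol gives no sample size or precision for objective h.

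**Assumptions, not in the protocol.** F4 share 10%, 20% or 30%; APRI sensitivity/specificity (Se/Sp) for F4 of 50%/90% or 70%/85%. The worked case is 20% F4 with 70%/85%.

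**Worked case, all 345 tested.** F4 = 0.20 × 345 = 69; below F4 = 276.

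- TP = 0.70 × 69 = 48.3; FN = 20.7
- TN = 0.85 × 276 = 234.6; FP = 41.4
- PPV = 48.3 / (48.3 + 41.4) = 53.8%
- NPV = 234.6 / (234.6 + 20.7) = 91.9%

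**Reading (a): AST only in F4.** TN = FP = 0.

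- Specificity = 0/0, undefined.
- PPV = 48.3/48.3 = 100% and NPV = 0/20.7 = 0%, whatever APRI's real accuracy.
- Only sensitivity for F4 is informative: 95% half-width 1.96 × √(0.70 × 0.30 / 69) = 10.8 points.
- Lower thresholds do not help, because an F4 patient is also positive at F1, F2 and F3.

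**Reading (b): AST in F4, or APRI at or above the cut-off.** The patients with APRI number 69 + 41.4 ≈ 110.

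- Everyone observed below F4 is APRI-positive, so specificity = 0/41.4 = 0 and NPV = 0/20.7 = 0 by construction.
- PPV at that cut-off = 48.3/89.7 = 53.8%, the true value, so it is estimable. Across the assumed range it runs from 34% to 68%.

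**Reading (c): AST in all F4 plus a random 25% of the rest.** FP = 0.25 × 41.4 = 10.35; TN = 0.25 × 234.6 = 58.65.

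- Specificity = 58.65/69 = 85%, unbiased only because selection is random; half-width 8.4 points.
- Naive PPV = 48.3 / (48.3 + 10.35) = 82.4%, against 53.8%.
- Naive NPV = 58.65 / (58.65 + 20.7) = 73.9%, against 91.9%.

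The same calculation over the assumed range:

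| F4 share (F4 / below F4) | Se/Sp | PPV, all tested | PPV, 25% tested | NPV, all tested | NPV, 25% tested |
|---|---|---|---|---|---|
| 10% (34 / 311) | 50/90 | 35.3% | 68.6% | 94.3% | 80.5% |
| 10% (34 / 311) | 70/85 | 33.8% | 67.1% | 96.3% | 86.6% |
| 20% (69 / 276) | 50/90 | 55.6% | 83.3% | 87.8% | 64.3% |
| 20% (69 / 276) | 70/85 | 53.8% | 82.4% | 91.9% | 73.9% |
| 30% (104 / 241) | 50/90 | 68.3% | 89.6% | 80.7% | 51.0% |
| 30% (104 / 241) | 70/85 | 66.8% | 89.0% | 86.8% | 62.1% |

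If clinicians choose whom to test on suspicion of advanced disease, specificity is biased as well.

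**After the fix.** With AST in all 345, all four measures are estimable. In the worked case the specificity half-width is 1.96 × √(0.85 × 0.15 / 276) = 4.2 points; over the range it is 3.3 to 4.5 points.

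**The case against.** A reader might infer that APRI will exist almost only in F4 patients and that specificity, NPV and PPV therefore cannot be estimated. The protocol does not support that, for these reasons:

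- Table 3.0 is a minimum. Footnote 1 states when AST is required and does not forbid it otherwise; footnotes 2 and 4 use the word *only* where a restriction is meant.
- The second trigger presupposes AST in some patients not yet classed F4. If it operates, PPV is estimable (reading b).
- The laboratory form accepts AST and APRI at any stage.
- No order of FibroScan before AST is fixed. Both sit in the Baseline column, and section 7 says the FibroScan machine moves between sites, so F4 status may be unknown when blood is drawn.
- The cohort includes untreated patients, some of whom may be treated later, so a missing AST is not always beyond recovery.
- Objective h is one of eleven secondary objectives, and section 6.VIII lists no APRI accuracy endpoint.

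All of this stands, and it limits the point to a risk for one secondary objective. It does not remove the conflict. A form completed only for received results does not order a test. The study relies on routinely collected data, and section 6.XI.a says nothing is collected beyond clinical management, so no research procedure fills the gap. AST beyond the minimum would then rest on local discretion, which is the selective testing in reading (c) or something worse.

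**Conclusion.** The point holds as a conflict between Table 3.0 footnote 1 and objective h with section 6.V. The required minimum does not secure APRI below F4, and one of the two AST triggers is circular. Followed literally, it leaves specificity undefined or zero and NPV zero by construction. PPV is either fixed at 100% or estimable, depending on whether the second trigger operates. With partial random testing of 25% below F4, naive PPV is overstated by about 21 to 33 points and naive NPV understated by about 10 to 30 points over the assumed range.

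These sizes rest on assumed F4 shares and APRI accuracy. The protocol does not show how often sites measure AST in practice; if they already do so in everyone, the harm largely disappears. SVR12, safety and eligibility analyses are unaffected. Severity: should-fix.

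**What to change.** For objective h, remove footnote 1 from the Baseline AST entry in Table 3.0, so that AST and its upper limit (item 413) are measured in every included patient alongside platelets and FibroScan. State in section 6.V that the comparison uses patients with all three at baseline. The footnote can stay on INR, bilirubin and albumin, which APRI does not use. If universal baseline AST is not wanted, restrict objective h to what the collected data can support, or drop it.

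The cost is one extra analyte for patients without cirrhosis, on a sample already drawn for ALT, at sites whose laboratories perform routine biochemistry (section 7). No extra visit is needed. If AST is not already routine in these patients, the statement in section 6.XI.a that nothing is collected beyond clinical management may need a matching edit.

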Appendix 4: Adverse Events Reporting Form

CRF AE_ N° Visit: _____

1_Surname: _____	2_Forename: _____	(not to enter in the database)
Patient's file N° _____		
3_ Identification cohort Number: _____ 4_ ID Key _____		

10_Date of consultation: ____ / ____ / ____ (dd/mm/yyyy)	12_Name of interviewer: _____	14_Data clerk initials: _____
11_Site of consultation: _____	13_Doctor / Clinical Officer / Nurse / Others	15_Date of data entry: ____ / ____ / ____ (dd/mm/yyyy)

Instructions: Only for the events leading to a change in the HCV treatment: change of drugs, change of dosage or interruption of treatment.
Fill all the questions. If the answer is unknown, tick the box DK (don't know)

Neurologic / Psychiatric			
501_Depression	 Yes	 No	 DK
502_Mania	 Yes	 No	 DK
503_Headache	 Yes	 No	 DK

Ocular / visual / hearing (from baseline)			
504_Eye disorders	 Yes	 No	 DK
505_Hearing Loss	 Yes	 No	 DK

Gastrointestinal			
506_Increase jaundice- hepatitis flare	 Yes	 No	 DK
507_Diarrhea	 Yes	 No	 DK
508_Nausea/ vomiting	 Yes	 No	 DK

Skin – Dermatological			
509_Rash	 Yes	 No	 DK
510_Photosensitivity	 Yes	 No	 DK
511_Hair loss	 Yes	 No	 DK

Musculoskeletal/ respiratory			
512_Cough/Respiratory Tract symptoms	 Yes	 No	 DK
513_Arthralgia/myalgia	 Yes	 No	 DK
514_Cardiologic problem	 Yes	 No	 DK

Endocrine / metabolic			
515_Diabetes Mellitus	 Yes	 No	 DK
516_Thyroid dysfunction	 Yes	 No	 DK

Biology anomaly			
517_Anemia	 Yes	 No	 DK
518_Neutropenia	 Yes	 No	 DK
519_Thrombocytopenia	 Yes	 No	 DK
520_Increase of ALT/AST	 Yes	 No	 DK

521_Other: specify _____

522_Pregnancy Yes No DK *If yes, fill the specific report form*

523_Is the Adverse event is considered as **Serious Adverse Event**: Yes No DK
If yes, fill the specific report form

Signature of the clinician _____

Transfer to Site Investigator (PI) Yes No DK

Date received by study PI ____ / ____ / ____ **Signature study PI** _____

Appendix 6

Management of the adverse effects

The main side effects associated with sofosbuvir are:
Sofosbuvir+ ribavirin - fatigue, headache, anaemia

Table 1. Treatment –emergent adverse events (all grades) reported in (> or = 15% of subjects in any treatment arm (Source Sovaldi package insert p.6)

Symptom	Interferon free regimen		
	Placebo 12 weeks N=71	SOF+RBV 12 weeks N=650	SOF+RBV 24 weeks N=250
Fatigue	24%	38%	30%
Headache	20%	24%	30%
Nausea	18%	22%	13%
Insomnia	4%	15%	16%
Pruritus	8%	11%	27%
Anemia	0%	10%	6%
Asthenia	3%	6%	21%
Rash	8%	8%	9%
Decreased appetite	10%	6%	6%
Chills	1%	2%	2%
Influenza Like Illness	3%	3%	6%
Pyrexia	0%	4%	4%
Diarrhea	6%	9%	12%
Neutropenia	0%	<1%	<1%
Myalgia	0%	6%	9%
Irritability	1%	10%	10%

Table 2: Management of adverse effects

Side effect	Comments	Suggested Management Strategies
GENERAL		
Fatigue	Fatigue is very common in patients with HCV and is probably increased on treatment with ribavirin. The following are not helpful in management of fatigue: dose reduction,	
 1. Check haemoglobin 2. Screen for depression 3. Suggest behavioural strategies to conserve energy e.g. rest periods, napping, planning ahead 4. Adequate fluid intake
Injection site reaction	Redness and induration are common. Occasionally painful nodules or ulceration may develop	
 1. Review technique for injection 2. Avoid painful or ulcerated areas

Side effect	Comments	Suggested Management Strategies
OTHER		
Respiratory Tract symptoms including shortness of breath	Ribavirin may be associated with cough.	
 1. Check haemoglobin (shortness of breath can occur with anemia); 2. CXR may be useful for persistent symptoms.
Rash	Itchy, dry, flaky skin is the most common abnormality due to treatment. It may resolve with time but will require treatment if severe.	
 1. Avoid powerful skin detergents and use regular non-perfumed skin moisturizers and sunblock during HCV treatment 2. If symptoms persist a low potency steroid cream (1% hydrocortisone) and antihistamine may be used (e.g. loratadine 10mg) 3. If severe and persistent a temporary reduction in the dose of RBV should be trialled.
Hearing Loss	Sudden loss of hearing and tinnitus have been described on treatment with ribavirin. The mechanism is unclear.	Hearing loss may not fully resolve after discontinuation of therapy but continuation of therapy may also not worsen symptoms.
AUTOIMMUNE DISEASES		
Diabetes Mellitus	Worsening of blood sugar control may occur on treatment for HCV	
 1. Counsel patients about the possibility of disturbances in glucose levels during treatment for HCV. 2. Advise to monitor blood sugar levels closely and medication dose adjustment may be required
increase of ALT/AST and/or jaundice-hepatitis flare	liver toxicity of all drugs in use	
 1. Consider liver toxicity of all drugs in use (record all drugs & doses in use + all drugs used last 7 days, plus alcohol consumption); 2. investigate HCV treatment failure with HCV VL & adherence; 3. investigate acute HEV infection (IgM & IgG; consider PCR if available) & HAV infection (IgM & IgG), 4. HBV treatment failure (check HBV viral load & treatment adherence); 5. HDV disease among HBsAg(+) including acute infection. 
Discuss all cases with HIV/TB/HCV advisor.

HAEMATOLOGICAL		
Anemia	Ribavirin causes haemolytic anemia and bone marrow suppression Usually occurs within 1-2 weeks of starting treatment in about 10% patients.	
 1. Management depends on baseline Hb and local normal range, availability of growth factors (e.g. erythropoietin), and whether patient has heart disease as anemia may worsen cardiac disease 2. If significant anemia occurs, the dose of ribavirin should be adjusted downwards by 200mg increments. 3. With improvements in Hb an attempt should be made to re-

Side effect	Comments	Suggested Management Strategies
		
increase the dose.
 
4. To avoid dose reductions associated with anemia, growth factors may be used if available.

Neutropenia	
No clear evidence exists that neutropenia during therapy has an adverse effect, nor that the use of G-CSF reduces rate of infections and/or improves SVR rates
	
Management depends on baseline neutrophil count, population normal range and the presence of other factors increasing the susceptibility to infection e.g. cirrhosis or HIV infection
 
See below

Thrombocytopenia		
Management depends on baseline platelet count and population normal range,
 
See below

